11 VISIT SCHEDULE AND ASSESSMENTS

11.1 Baseline Evaluation and Randomization Visit

A complete schedule of assessments throughout the study is given in Appendix B.

Study Visit 0 (Enrollment & Randomization **after LVAD implant**)
This visit will include the screening and informed consent process followed by a baseline assessment including:

- Demographic information
- Medical history including review of history of thromboembolism and atrial fibrillation
- Physical examination including height and weight
- Review of medications
- Local laboratory testing, including white blood cells, hemoglobin, platelet count, sodium, potassium, BUN, creatinine, magnesium, AST/ALT, total and direct bilirubin, albumin, total protein, alkaline phosphatase, activated partial thromboplastin time, prothrombin time/INR, LDH, fibrinogen, and d-dimer. Labs obtained within 1 week prior to randomization can be used to assess patient eligibility and apixaban dosing.
- Serum or urine pregnancy test on all women of childbearing potential
- Biobank blood collection
- Verification of listing status for transplant

At this visit, participants will be randomized to either apixaban or warfarin. Doses will be assigned in the following fashion:

In ambulatory patients assigned to warfarin, they will remain on their current warfarin dose adjusted to achieve an INR of 2.0-2.5.

For inpatients assigned to warfarin, warfarin dose will be determined based on the hospital protocol (Appendix A). Warfarin dose will be titrated and overlapped with heparin until an INR of 2.0-2.5 is reached.

In ambulatory patients randomized to apixaban a baseline INR will be obtained. Warfarin will be held until INR < 2.0 and the apixaban will be initiated at a dose of 5 mg BID.

For inpatients randomized to apixaban, apixaban will be initiated as first-line oral anticoagulation at a dose of 5 mg BID. Heparin will be discontinued at the time of apixaban initiation. No overlap should occur.

11.2 Follow-up Evaluations

Study Visit 1 (2 weeks post-randomization +/- 7 days) – Virtual Visit

At this visit, two weeks after randomization, interim history, review of medications, adherence and tolerance assessment, and adverse event monitoring.

Study Visit 2 (4 weeks post-randomization +/- 7 days)

At this visit, four weeks after randomization, interim history, review of medications, physical examination, laboratory testing (white blood cells, hemoglobin, platelet count, sodium, potassium, BUN, creatinine, magnesium, AST/ALT, total and direct bilirubin, albumin, total protein, alkaline phosphatase, activated partial thromboplastin time, prothrombin time/INR, LDH, fibrinogen, d-dimer and Anti-Xa level), adherence and tolerance assessment, and adverse event monitoring. A biobank blood collection will be performed. Verification of listing status for transplant to ensure ongoing eligibility for study participation.

Study Visit 3 (6 weeks post-randomization +/- 7 days) – Virtual Visit

At this visit, six weeks after randomization, interim history, review of medications, adherence and tolerance assessment, and adverse event monitoring.

Study Visit 4 (8 weeks post-randomization +/- 7 days) – Virtual Visit with Labs

At this visit, eight weeks after randomization, interim history, review of medications, adherence and tolerance assessment, and adverse event monitoring. Remote lab testing will include white blood cells, hemoglobin, platelet count, sodium, potassium, BUN, creatinine, magnesium, AST/ALT, total and direct bilirubin, albumin, total protein, alkaline phosphatase, prothrombin time/INR, LDH.

Study Visit 5 (12 weeks post-randomization +/- 14 days)

At this visit, 12 weeks after randomization, interim history, review of medications, physical examination, laboratory testing (white blood cells, hemoglobin, platelet count, sodium, potassium, BUN, creatinine, magnesium, AST/ALT, total and direct bilirubin, albumin, total protein, alkaline phosphatase, activated partial thromboplastin time, prothrombin time/INR, LDH, fibrinogen, d-dimer and Anti-Xa level), adherence and tolerance assessment, and adverse event monitoring. A biobank blood collection will be performed. Verification of listing status for transplant to ensure ongoing eligibility for study participation.

Study Visit 6 (18 weeks post-randomization +/- 14 days) – Virtual Visit

At this visit, eighteen weeks after randomization, interim history, review of medications, adherence and tolerance assessment, and adverse event monitoring.

Study Visit 7 (24 weeks after randomization +/- 14 days)

At this visit, 24 weeks after randomization, interim history, review of medications, physical examination, laboratory testing (white blood cells, hemoglobin, platelet count, sodium, potassium, BUN, creatinine, magnesium, AST/ALT, total and direct bilirubin, albumin, total protein, alkaline phosphatase, activated partial thromboplastin time, prothrombin time/INR, LDH, fibrinogen, d-dimer and Anti-Xa level), adherence and tolerance assessment, and adverse event monitoring. A biobank blood collection will be performed. Verification of listing status for transplant to ensure ongoing eligibility for study participation. After this visit, the study phase is complete.

At this visit patients will be provided the opportunity to continue open label apixaban therapy if randomized to apixaban arm of the study. Patients randomized to warfarin will continue warfarin therapy.

End of Study Visit or Visit 8 (28 weeks after randomization +/- 7 days) – Virtual Visit

At this visit, 28 weeks after randomization and 4 weeks after study drug completion, interim history, review of medications, and adverse event monitoring.

11.3 Phone and Other Media Follow-up

General procedures: At Study Visit 1, participants and study staff will define optimal times and phone numbers for the protocol-specified phone contacts to encourage compliance with study procedures. In addition video visit structure for follow-up study visits will be reviewed.

During the follow-up visits, the participant will receive:

- Reminder of appropriate study drug dose for the stage of the protocol.
- Confirm plans for future study visits
- Confirm need to bring study drug to future study visits.

12 OUTCOME DETERMINATIONS

12.1 Primary Endpoint

Freedom from death or hemocompatibility related adverse events (stroke, device thrombosis, bleeding, aortic root thrombus and arterial non-CNS thromboembolism) at 24-weeks.

12.2 Secondary Endpoints

- 1. Survival free of any stroke
- 2. Survival free of ischemic stroke
- 3. Survival free of hemorrhagic stroke
- 4. Survival free of device thrombosis
- 5. Survival free of aortic root thrombus
- 6. Survival free of gastrointestinal bleeding
- 7. Survival free of major non-gastrointestinal bleeding
- 8. All-cause mortality
- 9. Cardiovascular mortality

12.3 Tertiary Endpoints

- 1. Time in the therapeutic range for patients on warfarin
- 2. Anti-Xa trough concentration at 1 month, 3 months, and 6 months for patients on apixaban
- A subgroup analysis of above endpoints will be completed for patients enrolled immediately after LVAD implantation versus those enrolled ≥ 3 months from LVAD implantation

13 METHODS TO PROMOTE ADHERENCE

13.1 Protocol Training

Protocol training and adherence will be a major focus of the investigator training. Based on our experience in prior studies, identifying and correcting non-adherence is best accomplished in a stepped approach. The site will be responsible for managing participant compliance with study drug administration and visit compliance.

13.2 Data Quality Reports

The CC will provide data quality reports for review and will follow-up to reemphasize the importance of adherence as needed. Significant non-adherence issues will be discussed with the principal investigator.

14 SAFETY MONITORING AND REPORTING

14.1 Institutional Review Board

The study protocol, consent form, and other study documents will be subject to IRB approval. Any amendments to the protocol, other than minor administrative changes, must be approved by the IRB before they are implemented.

14.2 Definitions

14.1.1 Adverse Events

An adverse event (AE) is any untoward medical occurrence associated with the use of a drug in a participant, whether or not it is considered directly related to the drug or biologic related. An AE can therefore be any undesirable sign, symptom or medical condition occurring after starting study drug, even if the event is not considered to be related to the pharmaceutical product. Study drug includes the drug under evaluation, and any reference drug given during any phase of the trial. Safety monitoring for adverse events will begin upon randomization.

14.1.2 Suspected Adverse Reaction

A suspected adverse reaction (SAR) is any adverse event for which there is a reasonable possibility that the drug caused the event. "Reasonable possibility" suggests there is a causal relationship between the drug and the adverse event. "Suspected adverse reaction" implies a lesser degree of certainty about causality than adverse reaction, which means any adverse event caused by a drug.

14.1.3 Serious Adverse Events (SAE)

An adverse event or suspected adverse reaction is considered serious if the investigator or sponsor believes any of the following outcomes occurred:

- Death
- Life-threatening AE: Places the participant at immediate risk of death at the time
 of the event as it occurred. It does not include an AE that, had it occurred in a
 more severe form, might have caused death.
- Persistent or significant incapacity or substantial disruption of the ability to conduct normal life functions.
- Important medical events that may not result in death, be life threatening, or require hospitalization may be considered a serious adverse event when, based upon appropriate medical judgment, they may jeopardize the participant and may require medical or surgical intervention to prevent one of the outcomes listed in this definition above.

This determination is based on the opinion of either the investigator or sponsor (e.g., if either believes it is serious, it must be considered serious).

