14.1.6 Assessment of Adverse Event Severity

The determination of adverse event severity rests on medical judgment of a medically qualified Investigator. The severity of AEs will be graded using the following definitions:

- **Mild:** Awareness of sign, symptom, or event, but easily tolerated.
- **Moderate:** Discomfort enough to cause interference with usual activity and may warrant intervention.
- **Severe:** Incapacitating with inability to do usual activities or significantly affects clinical status, and warrants intervention.

Anticipated Disease Related Events and Events of Interest

The following are anticipated, disease-related events in patients with LVAD or anticipated events of interest in patients with apixaban or warfarin:

- Arrhythmias
- Cardiac Transplantation
- Device Explant
- Infection
- Transient Ischemic Attack
- Unplanned hospitalization, ER visit or clinic visit

Anticipated events will not be captured as AEs/SAEs during the study but will be entered on the appropriate electronic case report form (eCRF) module ("Anticipated Disease Related Events" page).

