14.1.9 Suspected Unexpected Serious Adverse Reaction

AEs that meet the criteria of serious, related to study drug, and unexpected per investigator brochure, qualify for expedited reporting to the regulatory authorities. The site Investigator will assess all SAE's occurring at his/her site and evaluate for "unexpectedness" and relationship to study drug. The site Investigator is required to complete and submit a voluntary MedWatch Report for events deemed, as serious, study drug related and unexpected at:

https://www.accessdata.fda.gov/scripts/medwatch/.

A copy of this report should be kept at the site.

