19.2 Appendix B - Adverse Event Definitions

- Arrhythmias: Any documented arrhythmia that results in clinical compromise, or requires hospitalization or treatment. Arrhythmias will be further classified as sustained ventricular arrhythmia or sustained supraventricular arrhythmia
- Arterial non-CNS thromboembolism: Acute systemic arterial perfusion deficit in any non-cerebrovascular organ system due to thromboembolism confirmed by 1 or more of the following: 1) standard clinical and laboratory testing, 2) operative findings, 3) autopsy findings
- Bleeding: the location/source of the bleed will be recorded and subsequently categorized as follows; CNS bleeding will be captured under cerebrovascular event/stroke
 - Type 2: Any overt, actionable sign of hemorrhage that does not fit the criteria for Type 3, 4, or 5 but does meet at least one of the following criteria:
 - 1) requiring non-surgical, medical intervention by a healthcare professional
 - 2) leading to hospitalization or increased level of care; or
 - 3) prompting evaluation
 - Type 3a
 - Overt bleeding accompanied by hemoglobin drop of 3 to < 5 g/dL
 - Any transfusion with overt bleeding
 - o Type 3b
 - Overt bleeding plus hemoglobin drop 5 g/dL or greater
 - Cardiac tamponade
 - Bleeding requiring surgical intervention for control (excluding dental/nasal/skin/hemorrhoid)
 - Bleeding requiring intravenous vasoactive agents
 - Type 4: VAD implantation-related bleeding (includes concomitant cardiac or non-cardiac surgical procedure)
 - Reoperation after the closure of incision or incisions used to implant the VAD to control bleeding
 - ≥ 50 kg: ≥ 4U pRBC within any 48 hours during the first 7 days postimplant
 - < 50 kg: ≥ 20 cm³/kg pRBC within any 24 hours during the first 7 days post-implant
 - Chest tube output > 2 liters within 24 hours
 - Type 5a: Probably fatal bleeding; no autopsy or imaging confirmation but clinically suspicious
 - Type 5b: Definite fatal bleeding; overt bleeding or autopsy or imaging confirmation
 - o For all types of bleeding, the event will be classified as:
 - Patient-related (e.g., coagulopathy unrelated to surgical technique such as non-adherence with anticoagulation medication resulting in inappropriately high level of anticoagulation, hepatic failure)
 - Management-related (e.g., related to surgical technique, hypertension, bleeding in the setting of inappropriate levels of anticoagulation)

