 - Pump-related (e.g., bleeding from the outflow graft, apical connector, or other internal components
- Major bleeding: Bleeding Types 3-5
- **Cerebrovascular event:** This refers to cerebrovascular accidents (stroke) of any cause (ischemic or hemorrhagic).
- Device Explant: This refers to LVAD explantation or LVAD decommissioning for myocardial recovery.
- Device Thrombosis: This refers to suspected or confirmed device thrombosis.
 - Suspected device thrombosis is a major device-related malfunction which clinical or device parameters suggest thrombus on the blood-contacting components of the pump, cannula, or grafts. Suspected device thrombosis will be defined as signs and symptoms to include at least 1 of the 3 following criteria:

- 1) Presence of major hemolysis by LDH or clinical evidence of hemolysis by hemoglobinuria
- 2) Presence of heart failure not explained by structural heart disease
- Abnormal pump parameters consistent with diminished pump output/pump efficiency/pump performance

And

- Suspected device thrombus will be accompanied by 1 or more of the following events or interventions:
 - 1) Death
 - 2) Stroke or TIA
 - 3) Arterial non-CNS embolism
 - 4) De-novo need for inotrope therapy
 - 5) Treatment with IV anticoagulation, IV thrombolytics, or IV antiplatelet therapy
 - 6) Pump replacement
 - 7) Pump explanation with or without exchange
 - 8) Pump deactivation without pump removal
 - 9) Operation to repair or replace any internal components of the circulatory support system
 - 10) Urgent transplant listing (immediate urgent listing for transplant)
- Confirmed device thrombosis is major device-related malfunction in which thrombus is confirmed within the blood-contacting surfaces of device inflow cannula or outflow conduit or grafts. This can be reported through direct visualization inspection or by incontrovertible contrast radiographic evidence or by the absence of an appropriate Doppler flow signal that results in or could potentially induce circulatory failure or result in thromboembolism
- **Gastrointestinal Bleeding:** This refers to bleeding from the gastrointestinal tract that is or is not identified.
- **Infection:** This refers to any infection requiring antibiotic or antifungal therapy.
- Transient Ischemic Attack: a transient neurologic deficit that may persist for up to 24 hours.
- **Unplanned hospitalization, ER visit or clinic visit:** This refers to any medical evaluation for an LVAD patient that is unplanned.

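### The serious adverse event definition leaves out hospitalization although its last bullet presupposes it, and unplanned admissions are exempted whatever their cause, so some can miss 24-hour and expedited reporting

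*Combined protocol and SAP*

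**What the plan says.** Section 14.1.3 gives four grounds for seriousness: death; a life-threatening event; "Persistent or significant incapacity or substantial disruption of the ability to conduct normal life functions"; and important medical events. The fourth bullet begins "Important medical events that may not result in death, be life threatening, or require hospitalization may be considered a serious adverse event". It applies to events that could endanger the participant and that "may require medical or surgical intervention to prevent one of the outcomes listed in this definition above". The section closes by making the opinion of either the investigator or the sponsor sufficient.

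The list of anticipated events that follows the severity grades in 14.1.6 includes "Unplanned hospitalization, ER visit or clinic visit". It then says "Anticipated events will not be captured as AEs/SAEs during the study" and sends these events to a separate eCRF page. Appendix B (19.2) defines the item: "This refers to any medical evaluation for an LVAD patient that is unplanned".

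Three reporting rules use these definitions:
- Section 14.1.7 keeps non-serious AEs off the safety reporting page, but puts events that force a change in antithrombotic dosing on the Adverse Events page.
- Section 14.1.8 requires SAEs to reach the IRB within 24 hours. It excepts the anticipated events from SAE capture and exempted events from that report.
- Section 14.1.9 states: "AEs that meet the criteria of serious, related to study drug, and unexpected per investigator brochure, qualify for expedited reporting".

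**The concern.** Seriousness is the condition for the 24-hour IRB report and one of three conditions for expedited reporting. If hospitalization is not a criterion, admissions short of the first three grounds become reportable only by discretion. If unplanned admissions are also exempt as a class, the discretion may not even be exercised, because the event can be filed as an anticipated one.

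This matters more here than in a trial of a drug with known risks in its population. The primary objective (4.1) is safety, treatment is open label (7.2), section 6 says no randomized trial has evaluated factor Xa inhibitors in LVAD patients, and 10.1.4 says the risks of apixaban in these patients are not known. A fixed criterion such as admission does not depend on the view of someone who knows the treatment; a judgment of medical importance does.

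**Working it through.** There is no figure to reproduce and no arithmetic applies. The check sets the sections side by side and follows an event through them.

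1. **Is hospitalization a listed criterion?** No. The list in 14.1.3 has four bullets, none of which names admission or prolongation of a stay.

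2. **Does the list assume that it is?** Yes. The fourth bullet is a residual clause for events that escape death, life threat and hospitalization. Such a clause makes sense only if all three are already criteria. Two are.

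3. **Does the fourth bullet fill the gap?** Only by judgment. Its wording is permissive, and it looks back to the outcomes listed above it. Since hospitalization is not among those, read literally it does not extend to an event whose treatment averts nothing worse than an admission.

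4. **What does the exemption add?** The anticipated item covers any unplanned medical evaluation, with no restriction by cause. Sections 14.1.6 and 14.1.8 then remove it from SAE capture and the 24-hour report. Neither section says that the diagnosis behind the admission stays reportable.

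5. **Follow two events, each leading to admission and neither fatal, life-threatening nor incapacitating.**

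| | Bleed | Unexpected event related to study drug |
|---|---|---|
| Meets one of the first three criteria | No | No |
| 24-hour IRB report (14.1.8) | Only if judged an important medical event | Only if judged an important medical event |
| Expedited report (14.1.9) | Ordinarily not due in any case, because bleeding is an expected reaction (10.1.4) | Only if judged an important medical event |
| Still recorded | Admission on the anticipated-events page; Adverse Events page if antithrombotic therapy changes | Admission on the anticipated-events page; Adverse Events page if antithrombotic dosing changes |

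Neither eCRF page in the last row carries a 24-hour clock.

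6. **Would one correction be enough?** No. If hospitalization were added to 14.1.3 alone, the exemption in 14.1.6 and 14.1.8 would still remove unplanned admissions. If the exemption alone were narrowed, admission would still not be a ground for seriousness. The three sections have to be reconciled together.

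**The case against.** The strongest reply is that little is lost. Bleeding, stroke, device thrombosis and arterial thromboembolism are not on the anticipated-events list, so the exemption can be read as covering only the admission. Section 14.1.8 changes antithrombotic therapy after a bleeding or thromboembolic event, so on a natural reading of 14.1.7 these events reach the Adverse Events page whether or not they are serious. Admissions have their own page. Either the investigator or the sponsor can declare an event serious. The follow-up text of 14.1.8 also asks for prompt AE reporting to the IRB under local requirements. Routing admissions separately may be deliberate in patients who are admitted often.

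Much of this stands: the data are recorded and the loss is possible, not automatic. It does not remove the defect. The narrow reading of the exemption is plausible but nowhere stated. If the omission is deliberate, the protocol does not say so, and the fourth bullet is still inconsistent. Local requirements are not given, and they are not the protocol's own 24-hour rule.

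A reader might infer four stronger points, which the documents do not support:

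- **That the DSMB would be misled.** The enrollment-pause triggers in 17.2 count thromboembolic events, Type 3-5 bleeds and deaths from either. None depends on SAE status. Section 17.1 has the DSMB review cumulative study data, not only SAEs.
- **That admitted bleeds escape expedited reporting.** Section 14.1.9 also requires unexpectedness. Section 10.1.4 names bleeding, including serious and fatal bleeding, as a reaction to both drugs.
- **That Appendix B downgrades admitted bleeds.** Type 2 does include bleeds "leading to hospitalization or increased level of care", but only those that miss Types 3 to 5. A bleed with any transfusion, or a hemoglobin drop of 3 g/dL or more, is Type 3 and so major. A bleeding grade is a separate matter from regulatory seriousness.
- **That 5 to 10 events are affected.** Taking the 25% first-year GI bleeding figure in section 5 as the rate, a constant hazard gives 1 - 0.75^(24/52) = 12.4%, or about 5 of 40 patients; placing all the risk within 24 weeks gives 0.25 x 40 = 10. This counts every GI bleed, not the admitted ones left to discretion. The 25% is also a ceiling, up to 20 patients may be enrolled 3 months or more after implant, past the period of most frequent bleeding, and 8.3 excludes patients with earlier post-LVAD GI bleeding.

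**Conclusion.** The point holds as an error in a reporting rule. Section 14.1.3 relies on a criterion it does not contain, and 14.1.6 and 14.1.8 exempt unplanned admissions without limit by cause. The events exposed are admissions that are not fatal, life-threatening or incapacitating and that neither investigator nor sponsor chooses to call important. Within that group, the 24-hour report can be missed for any event, and the expedited report only for events that are both related and unexpected.

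The size of the group cannot be estimated, because the documents give no admission rate and no rate for the discretionary subset. The conclusion does not need one. Bleeding and thromboembolic events are also components of the primary endpoint (12.1), defined there without reference to seriousness, so what is at risk is timely safety reporting.

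The conclusion assumes that the four bullets are the full list. The text was extracted from PDF and a lost bullet cannot be wholly excluded, but the list shows no gap or redaction mark and the sponsor can check this at once. Even with a restored bullet, the exemption would still need its limit stated.

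**What to change.** Make two changes together:

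1. In 14.1.3, add inpatient hospitalization or prolongation of existing hospitalization to the list, before the important-medical-events bullet, so that the bullet refers to a criterion that exists.
2. In the anticipated-events text of 14.1.6, and where 14.1.8 repeats the exemption, state that it covers the admission as such. It does not cover an underlying event that is bleeding, thromboembolism, device thrombosis or possibly related to study drug; that event is assessed for seriousness and reported in its own right.

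This is about two lines of text. It leaves treatment, visits, endpoints and analysis unchanged, and the anticipated-events page can stay as it is. The cost is a modest number of additional SAE reports, mostly admissions that would otherwise appear only on the anticipated-events or Adverse Events page.
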